1.0 Objectives

1.1 Study Objectives

The purpose of this study is to determine if an educational handout on birth control given in the prenatal period increases postpartum contraception use. In this randomized controlled trial, low-risk obstetric patients at 24-28 weeks gestational age will receive either an educational handout on contraception or a nutritional handout. Participants will be assessed at 8 weeks and 6 months postpartum regarding their contraception use. We hypothesize that a prenatal educational handout on contraception options will increase postpartum contraception use.

1.2 Primary Study Endpoints

The primary study endpoint is contraception use at 8 weeks postpartum.

1.3 Secondary Study Endpoints

The secondary study endpoints are contraception use at 6 months postpartum and method of contraception. In addition, we will assess patient satisfaction with prenatal contraception counseling and patient self-reported knowledge about contraception options.

2.0 Background

2.1 Scientific Background and Gaps

Reducing unintended pregnancies and those that are conceived within 18 months of a previous livebirth is an important health concern in the United States. Both unintended and close-interval pregnancies constitute 40% and 35% of pregnancies in the United States respectively with some overlap between the two categories and are associated with adverse maternal and fetal outcomes.¹ A national survey found that 17.8% of women using 'less-effective' methods and 23% of women using no birth control became pregnant in ≤ 18 months.² Access to better contraception education could potentially decrease the proportion of unintended pregnancies and close-interval pregnancies. In addition to the health concerns, 58% of women in the US would like more information about contraceptive options, and organized handouts on birth control have been shown to contribute to the choice in birth control.^{3,4}

However, there has been conflicting evidence about which educational methods increase postpartum contraception use.⁵⁻⁸ Therefore, we propose a randomized controlled trial (RCT) that assesses whether a handout on contraception options increases postpartum birth control use. The control group would receive a nutrition handout, and the intervention group would receive a handout on birth control options in addition to each receiving the standard of care. We will also give pre- and post-natal questionnaires, covering patient satisfaction, intention to use birth control, and how often a provider discusses birth control options.

2.2 Previous Data

There are currently no data analyzing 8-week postpartum contraception use in women who receive a standardized educational handout on birth control methods versus women who receive a standardized nutritional handout.

2.3 Study Rationale

The studies that have examined distributing educational materials on contraception have largely focused on unintended pregnancy rates. Furthermore, most of these studies did not use a recently postpartum population, which is one group that close-interval pregnancy can have severe and profound health effects on both the mother and the neonate. The few studies that did examine this population showed conflicting data as to which educational method was superior.

3.0 Inclusion and Exclusion Criteria

3.1 Inclusion Criteria

- 1) Women who are pregnant and are 24-28 weeks gestational age at the time of recruitment
- 2) Women >18 years of age
- 3) Women with low-risk pregnancies

3.2 Exclusion Criteria

- 1) Women who receive prenatal care solely at the Maternal Fetal Medicine department for high-risk pregnancies
- 2) Women who are members of an at-risk population including any women who is a prisoner, cannot provide consent, or is <18 years of age
- 3) Non-English speaking
- 4) No access to a valid email address.

3.3 Early Withdrawal of Subjects

3.3.1 Criteria for removal from study

Patients will be withdrawn from the study should they deliver prior to 34 0/7 weeks gestational age or have a fetal demise, postpartum course complicated by an ICU stay, or receive an emergency hysterectomy at delivery. Patients will also be withdrawn if they fail to complete key components of the intake survey (i.e. name, date of birth, email address, or obstetric history) or the 8-week postpartum survey. Patients will be contacted by email and/or telephone. Should a patient fail to respond to these attempts at contact, they will be presumed to have withdrawn from the study. Additionally, any patient can withdraw from the study at any point upon their request. As this is a low-risk trial, we do not anticipate any patients being withdrawn for safety reasons or adverse health outcomes.

3.3.2 Follow-up for withdrawn subjects

At any point upon subject request or upon failure to complete surveys, patients will be withdrawn from the study. No further data will be collected on withdrawn subjects, and there will be no additional follow-up beyond the postpartum standard of care. Following the withdrawal of a subject, that individual will not be replaced in this study.

4.0 Recruitment Methods

4.1 Identification of subjects

Patients seen for prenatal care between 24-28 weeks gestation in the Obstetrics and Gynecology clinics at [name], [name] and [name] will be approached regarding participation in this study as part of their appointment.

4.2 Recruitment process

4.2. 1 How potential subjects will be recruited.

Patients will be approached in-person about participation in this study during their clinical visit.

4.2. 2 Where potential subjects will be recruited.

[name], [name] and [name] OB/Gyn offices.

4.2. 3 When potential subjects will be recruited.

During or after their 24-28-week pregnancy visit, which is a standard and pre-appointed visit during all pregnancies.

4.2. 4 Describe the eligibility screening process and indicate whether the screening process will occur before or after obtaining informed consent. Screening begins when the investigator obtains information about or from a prospective participant in order to determine their eligibility. In some studies, these procedures may not take place unless HIPAA Authorization is obtained OR a waiver of HIPAA Authorization when applicable for the screening procedures is approved by the IRB.

Patient schedules and medical records will be reviewed for eligibility prior to obtaining informed consent.

5.0 Consent Process and Documentation

5.1 Consent Process:

Check all applicable boxes below:

X Informed consent will be sought and documented with a written consent form *[Complete Sections 5.2 and 5.6]*

Implied or verbal consent will be obtained – subjects will not sign a consent form (waiver of written documentation of consent) *[Complete Sections 5.2, 5.3 and 5.6]*

Informed consent will be sought but some of the elements of informed consent will be omitted or altered (e.g., deception). *[Complete section 5.2, 5.4 and 5.6]*

Informed consent will not be obtained – request to completely waive the informed consent requirement. *[Complete Section 5.5]*

The following checkbox is for all locations EXCEPT Penn State Health and College of Medicine:

Exempt Research at all Locations Except Penn State Health and the College of Medicine: If you believe that the research activities outlined meet one or more of the criteria outlined in "HRP-312- Worksheet- Exemption Determination." Please verify by checking this box that if conducting an exempt research study, the consent process will disclose the following (all of which are included in "HRP-590- Consent Guidance for Exempt Research"):

Penn State affiliation; name and contact information for the researcher and advisor (if the researcher is a student); the activities involve research; the procedures to be performed; participation is voluntary; that there are adequate provisions to maintain the privacy interests of subjects and the confidentiality of the data; and subjects may choose not to answer specific questions.

If the research includes the use of student educational records include the following language in this section (otherwise delete): The parent or eligible student will provide a signed and dated written consent that discloses: the records that may be disclosed; the purpose of the disclosure; the party or class of parties to whom the disclosure may be made; if a parent or adult student requests, the school will provide him or her with a copy of the records disclosed; if the parent of a student who is not an adult so requests, the school will provide the student with a copy of the records disclosed.

Note: If this box has been checked, skip the remainder of section 5 and proceed to section 6 of this protocol. If the investigator's assessment is inaccurate, an IRB Analyst will request revision to the protocol and that an informed consent form be submitted for review and approval. Except for exemptions where Limited IRB Review (see "HRP-312- Worksheet- Exemption Determination") is required or where otherwise requested by the IRB, informed consent forms for research activities determined to be exempt without Limited IRB Review are generally not required to be submitted for review and approval by the University Park IRB.

5.2 Obtaining Informed Consent

5.2. 1 Timing and Location of Consent

Informed consent will be obtained at the patient's prenatal appointment at 24-28 weeks gestation. These appointments will take place at [name], [name] and [name] on the Penn State Health campuses where the Obstetrics and Gynecology service has clinic.

5.2. 2 Coercion or Undue Influence during Consent

Consent will be obtained at the prenatal appointment from 24-28 weeks gestation. Patients will be informed verbally and in writing that participating in this study is entirely voluntary and that medical care is not contingent on agreeing to participate in this study.

5.3 Waiver of Written Documentation of Consent

N/A

5.3. 1 Indicate which of the following conditions applies to this research:

The research presents no more than minimal risk of harm to subjects and involves no procedures for which written consent is normally required outside of the research context.

OR

The only record linking the subject and the research would be the consent document and the principal risk would be potential harm resulting from a breach of confidentiality. Each subject will be asked whether the subject wants documentation linking the subject with the research, and the subject's wishes will govern. (Note: This condition is not applicable for FDA-regulated research. If this category is chosen, include copies of a consent form and /or parental permission form for participants who want written documentation linking them to the research.)

OR

- If the subjects or legally authorized representatives are members of a distinct cultural group or community in which signing forms is not the norm, that the research presents no more than minimal risk of harm to subjects and provided there is an appropriate alternative mechanism for documenting that informed consent was obtained. (*Note: This condition is not applicable for FDA-regulated research.*)

5.3. 2 Indicate what materials, if any, will be used to inform potential subjects about the research (e.g., a letter accompanying a questionnaire, verbal script, implied consent form, or summary explanation of the research)

N/A

5.4 Informed consent will be sought but some of the elements of informed consent will be omitted or altered (e.g., deception).

5.4. 1 Indicate the elements of informed consent to be omitted or altered

N/A

5.4. 2 Indicate why the research could not practicably be carried out without the omission or alteration of consent elements

N/A

5.4. 3 Describe why the research involves no more than minimal risk to subjects.

N/A

5.4. 4 Describe why the alteration/omission will not adversely affect the rights and welfare of subjects.

N/A

5.4. 5 If the research involves using identifiable private information or identifiable biospecimens, describe why the research could not be practicably be carried out without using such information or biospecimens in an identifiable format.

N/A

5.4. 6 Debriefing

N/A

5.5 Informed consent will not be obtained – request to completely waive the informed consent requirement

N/A

5.6 Consent – Other Considerations

5.6. 1 Non-English-Speaking Subjects

Non-English-speaking subjects will not be included.

5.6. 2 Cognitively Impaired Adults

5.6.2.1 Capability of Providing Consent

N/A

5.6.2.2 Adults Unable to Consent

N/A

5.6.2.3 Assent of Adults Unable to Consent

N/A

5.6. 3 Subjects who are not yet adults (infants, children, teenagers)

5.6.3.1 Parental Permission

N/A

5.6.3.2 Assent of subjects who are not yet adults

N/A

6.0 HIPAA Research Authorization and/or Waiver or Alteration of Authorization

6.1 Authorization and/or Waiver or Alteration of Authorization for the Uses and Disclosures of PHI

Check all that apply:

- Not applicable, no identifiable protected health information (PHI) is accessed, used or disclosed in this study. [Mark all parts of sections 6.2 and 6.3 as not applicable]**
- Authorization will be obtained and documented as part of the consent process. [If this is the only box checked, mark sections 6.2 and 6.3 as not applicable]**
- Partial waiver is requested for recruitment purposes only (Check this box if patients' medical records will be accessed to determine eligibility before consent/authorization has been obtained). [Complete all parts of sections 6.2 and 6.3]**
- Full waiver is requested for entire research study (e.g., medical record review studies). [Complete all parts of sections 6.2 and 6.3]**
- Alteration is requested to waive requirement for written documentation of authorization (verbal authorization will be obtained). [Complete all parts of sections 6.2 and 6.3]**

6.2 Waiver or Alteration of Authorization for the Uses and Disclosures of PHI

6.2. 1 Access, use or disclosure of PHI representing no more than a minimal risk to the privacy of the individual

6.2 .1.1 Plan to protect PHI from improper use or disclosure

Information is included in the “Confidentiality, Privacy and Data Management” section of this protocol.

6.2 .1.2 Plan to destroy identifiers or a justification for retaining identifiers

Data will be stored in a secure web application as outlined below. Data will be de-identified with removal of PHI when abstracted and stored on a secure server for statistical analysis.

6.2. 2 Explanation for why the research could not practicably be conducted without access to and use of PHI

Without PHI, it would be impossible to identify patients who would be eligible for this study.

6.2. 3 Explanation for why the research could not practicably be conducted without the waiver or alteration of authorization

Without the ability to access the medical records of patients, it would be impossible to perform the prospective nature of this study.

6.3 Waiver or alteration of authorization statements of agreement

Protected health information obtained as part of this research will not be reused or disclosed to any other person or entity, except as required by law, for authorized oversight of the research study, or for other permitted uses and disclosures according to federal regulations.

The research team will collect only information essential to the study and in accord with the ‘Minimum Necessary’ standard (information reasonably necessary to accomplish the objectives of the research) per federal regulations.

Access to the information will be limited, to the greatest extent possible, within the research team. All disclosures or releases of identifiable information granted under this waiver will be accounted for and documented.

7.0 Study Design and Procedures

7.1 Study Design

Prospective randomized controlled trial.

7.2 Study Procedures

7.2.1 Timepoint 1: At 24-28 weeks gestation

At patients’ previously-scheduled prenatal appointment at 24-28 weeks gestational age, patients will receive a research-specific packet to include demographic questionnaire and proprietary questionnaire after determining the individual’s eligibility and obtaining informed consent. A cover letter will be provided to the patients briefly describing the study and their requested

participation. After obtaining proper consent and signing the necessary forms, patients will complete the demographic information found on the intake questionnaire in paper form. After completion of the initial demographic information (i.e. name, date of birth, email address, and mailing address), the patient will be randomized (randomization will be stratified by recruitment location) to either group A or B via REDCap and receive a sealed envelope containing the respective handout. The envelopes will simply be labeled “A” or “B” so that the study personnel are blinded to the allocation. The envelopes will be assembled by an individual outside of the study team who will determine the handout designations for A and B. A master copy of one sealed ‘A’ envelope and one sealed ‘B’ envelope will be provided to the statisticians; these envelopes will be opened at the end of the study to unblind the groups. Following randomization, the patient will receive her intake questionnaire with her demographic information already filled in to be completed during this visit. The completed intake questionnaire will then be returned and stored in a locked and secured location. These survey results will be compiled, entered, and stored under the Redcap database.

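### The intake questionnaire is finished after randomisation, with the handout envelope in hand, so subjective intake answers are not assured to be baseline and a blank obstetric history can remove a randomised woman (minor, cheap to avoid)

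*Combined protocol and SAP*

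**What the plan says.** Section 7.2.1 sets out the recruitment visit. After consent, "patients will receive a research-specific packet to include demographic questionnaire and proprietary questionnaire". The allocation step depends on a short list of items: "After completion of the initial demographic information (i.e. name, date of birth, email address, and mailing address), the patient will be randomized". At that point she is assigned through REDCap and will "receive a sealed envelope containing the respective handout". The remainder of the form is timed by one sentence only: "Following randomization, the patient will receive her intake questionnaire with her demographic information already filled in to be completed during this visit". The envelopes are labelled A or B to blind study personnel. No section says that the woman must keep hers closed until the form is returned.

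The intake form itself is not in the documents. Section 2.1 hints at its content: "We will also give pre- and post-natal questionnaires, covering patient satisfaction, intention to use birth control". It does not say which items are on which form. Section 1.3 lists related secondary endpoints: "we will assess patient satisfaction with prenatal contraception counseling and patient self-reported knowledge about contraception options".

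Section 3.3.1 makes it a ground for withdrawal not to complete "key components of the intake survey (i.e. name, date of birth, email address, or obstetric history". Under section 3.3.2, no more data are collected on a withdrawn woman and she is not replaced. Section 3.3.1 adds: "Patients will be contacted by email and/or telephone". It does not say whether that contact extends to a blank intake item.

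The only test specified (section 8.3) is an unadjusted two-sided chi-square on contraception use at 8 weeks.

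**The concern.** A baseline form is normally closed before allocation, for two reasons. Answers given afterwards may be influenced by the treatment, and incomplete forms cease to be a screening matter and become losses from the randomised groups. This plan leaves both doors open.

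- **Subjective answers.** The intervention is the handout, and the woman holds it while she completes the form. Items such as intention to use birth control could be changed by reading it. If those answers were later reported or used as baseline, they might not be baseline in the contraception arm. Factual items, such as previous contraception use, are unlikely to be affected.
- **Withdrawals.** A woman who leaves obstetric history blank could lose her primary outcome because of an item that is neither the endpoint nor part of the specified test.

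**Working it through.** **Order of the key items.** Of the four key intake items in section 3.3.1, name, date of birth and email address are on the pre-randomisation list in section 7.2.1. Obstetric history is not. So it is the one item through which an incomplete intake form can remove a woman who has already been randomised.

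**The plan's own sample size.** Inputs from sections 8.1 and 8.2: 0.75 versus 0.90, two-sided 0.05, 80% power, 10% drop-out. With pooled variance and mean proportion 0.825:

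- n per arm = [1.960·√(2·0.825·0.175) + 0.842·√(0.75·0.25 + 0.90·0.10)]² / 0.15² = 99.5, rounded up to 100.
- 100/0.90 = 111.1, rounded up to 112 per arm, or 224 in total.

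Both figures match the plan.

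**Power if obstetric-history blanks are withdrawn.** The documents give no rate, so 1%, 2% and 5% are assumed. Of 224 women these are about 2, 4 and 11. After the planned drop-out, 224·0.90/2 = 100.8 per arm remain. Power = Φ{[0.15·√n − 1.960·√(2·0.825·0.175)] / √(0.75·0.25 + 0.90·0.10)}.

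| Scenario | 1% blank | 2% blank | 5% blank |
|---|---|---|---|
| Blanks already within the 10% | 80.5% | 80.5% | 80.5% |
| Blanks on top (n × 0.99, 0.98, 0.95) | 80.1% | 79.7% | 78.4% |
| On top, half recovered by contact (n × 0.995, 0.99, 0.975) | 80.3% | 80.1% | 79.5% |

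**Type I error.** This is the exact rejection rate of the uncorrected chi-square with no true effect, 75% use in both arms, 101 per arm, and exclusions occurring at random at rate f. With no exclusions it is 4.96%.

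| Pattern of exclusions | f = 1% | f = 2% | f = 5% |
|---|---|---|---|
| One arm, unrelated to use | 5.02% | 5.03% | 5.04% |
| Both arms alike, half non-users | 5.03% | 5.04% | 5.03% |
| Both arms alike, all non-users | 5.03% | 5.05% | 5.02% |
| One arm only, half non-users | 5.04% | 5.11% | 5.56% |
| One arm only, all non-users (extreme bound) | 5.20% | 5.76% | 10.06% |

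The spurious differences behind the last two rows, against a planned difference of 15 points, are:

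- half non-users: (0.75 − 0.5f)/(1 − f) − 0.75 = 0.3, 0.5 and 1.3 points;
- all non-users: 0.75/(1 − f) − 0.75 = 0.8, 1.5 and 3.9 points.

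**Subjective item.** Assume that an intention item is on the form and that 70% intend to use birth control. Assume also that 0 to 50% of the contraception arm read the handout first, and that 10 to 25% of the non-intenders among them change their answer. The arms then differ by 0.30 × read × change, which runs from 0 to 0.30·0.50·0.25 = 3.75 points. Chance alone allows about 1.96·√(2·0.7·0.3/112) = 12.0 points with 112 per arm.

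**The case against.** The strongest reply concerns materiality, not fact.

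The subjective-answer limb has no consequence in the plan as written. Section 8.3 uses no intake variable, and section 1.3 does not define satisfaction or knowledge as change from intake. For harm to arise, the form must carry subjective items, women must open a sealed envelope during the visit before returning the form, and someone must later use the answers as baseline. None of these is shown in the documents. This stands, and limb one is therefore conditional.

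The withdrawal limb concerns one field on a form that is completed and returned at a clinic visit. Staff could notice a blank, contact by email or telephone might recover it, and the 10% allowance may already cover it. These are fair points, but no check is written down, and section 3.3.1 does not say that contact covers intake items.

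The 10.06% bound needs 5% blanks, all in one arm and all among later non-users. With 75% use, that is 5/25, or one in five non-users in that arm and none in the other. The documents offer no mechanism for this, so the bound should carry no weight as an expectation.

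Finally, withdrawal for not completing the 8-week survey, also in section 3.3.1, is a much larger exclusion of the same kind, and reordering the intake form does not touch it. That is true, but it is a separate matter.

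**Conclusion.** The concern holds, as a minor one. The sequence in section 7.2.1 is explicit, and no other section corrects it or says when the envelope may be opened.

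For the primary analysis, the likely cost is at most about two points of power (80.5% to 78.4%) at an assumed 5% blank rate, and none if the drop-out allowance already covers blanks. Type I error stays at about 5.0% when exclusions are unrelated to use or occur alike in both arms, and the documents give no reason to expect otherwise. The effect on subjective intake answers depends on a form that is not shown and, under the assumptions above, lies well inside chance variation.

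The case for change is that both problems can be avoided at almost no cost, not that either is large. All blank, reading and answer-change rates are assumptions.

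**What to change.** In section 7.2.1, have the whole intake questionnaire completed, checked for the key items of section 3.3.1 and returned before REDCap randomisation and before the envelope is handed over. Women with incomplete forms are then not randomised, and the intake-survey ground can be deleted from section 3.3.1.

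If the order cannot change, two smaller steps serve:

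- Tell the woman to keep the envelope closed until the form is returned. This protects the subjective answers but does not remove the withdrawal ground.
- Before treating her as withdrawn, take a missing obstetric history from the medical record, which is already reviewed before consent (section 4.2.4) and at 8 weeks (section 7.2.2).

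The cost is one reordered step at the same visit, about two sentences of text, and a slightly longer wait before randomisation. If 224 is to be the number randomised, blanks of 1%, 2% or 5% mean consenting 224/0.99, 224/0.98 or 224/0.95 women. Rounded up, that is 227, 229 or 236, or 3, 5 or 12 more. Against the 979 deliveries at one office (section 15.2), the share rises at most from 224/979 = 22.9% to 236/979 = 24.1%. Two further offices also recruit, so the real burden is lower.
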